## **Risks and Benefits**

- I. Risks
- A. Anticipated medical risks
1. After OMT, muscle tenderness and generalized discomfort may be noted 24-48 hours after treatment in a small number of patients.
  2. There is little empirical data about the “hazards” to patients of student-performed procedures. Further, this study does not employ any inherently forceful techniques (such as high velocity low amplitude HVLA).
  3. There are no anticipated adverse effects associated with BEMER therapy. In addition, we have already utilized the BEMER therapy in a prior study on low back pain. No adverse effects were noted.
- B. Steps taken to minimize the risks
1. All Osteopathic Medical students performing osteopathic manipulation will receive additional special training by a licensed osteopathic physician, member of the LECOM-Bradenton OMM Department, and will disclose their true identity to the subjects to avoid any misconceptions that they are licensed physicians. Student-treaters will be critiqued by a physician until they are approved to perform OMT on the subjects.

2. A licensed osteopathic physician will be in the vicinity of the treatment location at all times a treatment is being given. [name] will be in the building and, if not in the treatment room, will be available by phone and/or text message at all times during treatments and will respond immediately to matters involving the study participants and/or treatments.
  3. All treatments will be performed by osteopathic medical students. [name] will provide students additional training on OMT and placebo treatments, and [name], a BEMER representative, will provide additional training on BEMER treatments.
  4. There are no funds designated to compensate subjects for injury. The principal investigator will work with injured subjects to provide them with further information to the best of his ability.
- C. Plan for reporting adverse events
1. All serious or unanticipated adverse events will be reported to the LECOM IRB promptly.
  2. All protocol amendments will be submitted to the IRB for approval, with the exception of changes that must be made in order to eliminate any imminent risk of harm to subjects or to others. In this circumstance, the investigator will act to eliminate the immediate risk but must subsequently submit an appropriate protocol amendment and await approval before proceeding with the revised protocol.
- II. Benefits
- A. Description of probable benefits
1. Subjects may experience a decrease in neck pain. This can translate to healthy and natural ways to improve quality of living in patients with disabling neck pain. Individually, patients could see significant increases in quality of life.
  2. With regards to society, this study could provide patients with an efficient and inexpensive way to alleviate many of the disabilities that are associated with living with neck pain.

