position and then rotate the head and neck to one side. This position will be held for 30 seconds. If at any time the subject complains of dizziness, visual changes, lightheadedness and/or the evaluating student notes eye nystagmus then this is considered a positive test. A positive test will exclude the subject from the study. The test is performed bilaterally [27].

E. Bio Electro-Magnetic Energy Regulation (BEMER)

1. Protocol

a) Subject will lay supine on the BEMER mat, and place the B.Pad® on their cervical neck. BEMER mat intensity 3 will be selected in week 1, intensity 4 for week 2, and intensity 5 for week 3. B.Pad® will be set at Program 1 for the duration of the intervention. Treatments last approximately 15-25 minutes.

2. Explanation of BEMER

a) BEMER is a therapeutic modality that deploys a biorhythmically defined stimulus through Pulsed Electromagnetic Field (PEMF). This stimulus has a targeted effect on the microvasculature, and the primary effect is an improvement in tissue microcirculation [9]. The positive effects of vasomotion (i.e. opening of the blood vessels) on the microcirculation has been shown to result in significant increases in arteriovenous oxygen difference, number of open capillaries, arteriolar and venular flow volume, and flow rate of red blood cells in the microvasculature [7, 8]. Therefore, BEMER can potentially be used in the treatment of neck pain by improving microcirculation in muscular tissue. Last year we have successfully utilized the BEMER therapy without any adverse effects in a prior study on low back pain.

F. Placebo

1. Placebo (Combined light touch and BEMER Sham): Treaters will place their hands lightly on the subject's cervical paraspinal muscles in the supine position in the same area as one would place their hands for cervical MFR, and on the subjects upper thoracic paraspinal muscles in the prone position in the same area as one would place their hands for thoracic MFR (approximately 5 minutes). However, no pressure or action will be done. In addition, the subject will lie down on the BEMER mat (as they would do during a BEMER session), but the device will not be activated. This treatment will be used as a control.

G. The research assistants will individually coordinate experimental times with the subjects. A licensed osteopathic physician will be in the vicinity of the treatment location at all times while treatments are being given.

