H. OMT, BEMER, and placebo will be performed by osteopathic medical students who have completed additional training given by a licensed osteopathic physician to ensure uniform technique. A licensed osteopathic physician will be in the vicinity of the treatment location at all times while treatments are being given.

I. All data collection logs will be de-identified of personal information and only contain the randomized participant ID number linking the participant to the data collected.

J. The identifying information will be maintained by the principal investigator in a locked cabinet, which they alone have access to.

II. Study Procedures and Timeline

A. Study duration

1. The study duration is three weeks. The subjects will be required to have either OMT, BEMER, OMT+BEMER, or Placebo treatments during the course of the study. Each subject in the OMT groups (i.e. OMT and OMT+BEMER) will receive treatment 3 times per week for a period of 3 weeks. Subjects in the BEMER groups (i.e. BEMER and OMT+BEMER) will receive treatment 5 times per week for a period of 3 weeks. Finally, subjects in the Placebo group will receive the combined light touch and BEMER sham treatments at same intervals as the corresponding experimental groups. OMT, BEMER, and placebo treatments will be performed by osteopathic medical students who have completed additional training given by a licensed osteopathic physician, to ensure uniform technique.
2. Recruitment:
  - a) LECOM-Bradenton faculty, staff, osteopathic medical, dental, pharmacy, and master's students will be informed via email of the opportunity to participate in the research study and will be given contact information to confirm eligibility with a study coordinator (Appendix A).
3. Experimental Sessions
  - a) Following written consent (Appendix B), subjects will be given a randomized study ID number. They will be randomized into their treatment group.

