  - b) Each subject in the OMT groups (i.e. OMT and OMT+BEMER) will receive treatment 3 times per week for a period of 3 weeks. As previously mentioned, subjects in the BEMER groups (i.e. BEMER and OMT+BEMER) will receive treatment 5 times per week for a period of 3 weeks. Finally, subjects in the Placebo group will receive the combined light touch and BEMER sham treatments at same intervals as the corresponding experimental groups. OMT, BEMER, and placebo treatments will be performed by osteopathic medical students who have completed additional training given by a licensed osteopathic physician, to ensure uniform technique. All treatments will be performed during the span of three consecutive weeks.
  - c) Subjects will complete brief questionnaires regarding neck pain and quality of life before the beginning of study and will complete the same questionnaires following the completion of the three week treatment (Appendices C, E, F).

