#### II. Exclusion

A. Subjects will be excluded if they are unable to provide informed consent, are currently pregnant, have a positive screening test (listed above) or have a known medical history of any of the following:

1. Psychiatric conditions
2. Skin disorders or open wounds precluding skin contact
3. Fasciitis or fascial tears
4. Myositis
5. Neurological symptoms such as numbness, tingling, weakness in upper extremities
6. Neoplasia
7. Bone fracture, osteomyelitis, or osteoporosis
8. Coagulation problem
9. Deep vein thrombosis
10. Adrenal diseases/syndromes
11. Acute upper or lower respiratory infection
12. Immunosuppressive syndromes
13. Radiation or chemotherapy within the past 3 years
14. Lupus
15. Osteopenia
16. Congestive heart failure
17. BMI greater than 30

18. Any other autoimmune disease not stated above
  19. Medication changes within the last 4 weeks
  20. Asthma exacerbations within the last 4 weeks
  21. Immunosuppressive therapy as a consequence of organ transplantation
  22. Immunosuppressive therapy as a consequence of allogeneic cellular transplantations or bone marrow stem cell transplantation
  23. Other conditions often requiring immunosuppressive therapy
  24. Anticoagulant therapy
  25. Known sensitivity to the carotid sinus reflex
  26. Advanced carotid disease
  27. Down syndrome
- B. Subjects will be screened for eligibility based on the inclusion and exclusion criteria described above at the point of subject consent. No protected health information will be collected from subjects who are not eligible to participate in the study.
- C. If subjects develop any of the above issues during the course of the study, they will be removed from the study without penalty and will still receive compensation.
- D. All female patients will be screened in the selection process by self-report as to whether or not they are pregnant. Under any suspicion of pregnancy, the participant will be ineligible for participation.
- III. Definition of treatment failure or subject removal criteria
- A. Subjects who do not adhere to the full treatment regimen will be removed from the study.
- B. Subjects who experience any adverse effects from treatment, as determined by a licensed osteopathic physician, will be immediately removed from the study. However, we do not anticipate any adverse effects during the study. Last year we have successfully utilized OMT and the BEMER therapy without any adverse effects in a prior study on low back pain.

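### The reaction the protocol expects 24 to 48 hours after OMT is captured only if volunteered; one short symptom item at each visit and after the last would collect it

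*Combined protocol and SAP*

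**What the plan says.** Risks and Benefits, I.A.1 names one expected reaction and its timing: "After OMT, muscle tenderness and generalized discomfort may be noted 24-48 hours after treatment in a small number of patients". The only reporting procedure, in I.C.1 of the same section, is: "All serious or unanticipated adverse events will be reported to the LECOM IRB promptly".

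Participant-reported data are described in Study Procedures and Timeline, II.A.3.c: "Subjects will complete brief questionnaires regarding neck pain and quality of life before the beginning of study". The forms are repeated once the three weeks are over. Analysis, III.A.1 lists these forms as the NDI, SF-12 and VAS. The interval between the last session and the second set of forms is not given. Methodology, I.B places post-treatment measurements in the laboratory.

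Two rules depend on adverse effects that a physician has identified. One is the early stopping rule in Analysis, III.A.3. The other is the removal rule in Research Participants, III.B: "Subjects who experience any adverse effects from treatment, as determined by a licensed osteopathic physician, will be immediately removed from the study". Both places add that no adverse effects are expected.

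The visit schedule in II.A.1 differs by arm. For OMT it reads: "Each subject in the OMT groups (i.e. OMT and OMT+BEMER) will receive treatment 3 times per week for a period of 3 weeks". Both arms that include BEMER have five BEMER sessions weekly over the same three weeks. The control arm is described thus: "subjects in the Placebo group will receive the combined light touch and BEMER sham treatments at same intervals as the corresponding experimental groups".

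**The concern.** The protocol names a delayed, mild reaction and then gives no means of asking about it. It is expected and not serious, so it falls outside the IRB reporting rule. No diary, symptom log, safety call or safety tabulation appears in the available text. Physician cover is tied to treatment times, while the reaction is expected a day or two later.

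Three things are at stake.

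- The stopping and removal rules can act only on what reaches the physician, which without elicitation means what participants choose to mention.
- A participant who gives up because of soreness and is never assessed looks non-adherent. Such a participant is removed under Research Participants, III.A and unpaid under Payment and Costs, I.C, whereas one withdrawn for an adverse event is paid under I.B. If the reaction is specific to OMT, such losses would fall mainly in the OMT arms.
- A closing statement that no adverse effects occurred would carry little information. Risks and Benefits, I.A.2 itself notes how little is known about the hazards of student-performed procedures.

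**Working it through.** **Figures in the plan.** The documents give no harm rate, safety sample size or precision target, so there is no safety figure to reproduce. The sample size is consistent: 4 groups × about 10 = 40, and the budget gives $2,000 / $50 = 40.

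**What each existing route could catch.**

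| Route | What it covers | What it misses |
|---|---|---|
| VAS, NDI section 1 | Pain at the moment of completion, all arms | A reaction that has resolved; whether the pain is new or the entry complaint |
| SF-12 item 8 | Interference from pain over four weeks, all arms | Pools the entry neck pain with any reaction to treatment |
| IRB reporting | Serious or unanticipated events | The expected, non-serious reaction |
| Physician determination | Events brought to the physician | Anything not volunteered; whether expected tenderness counts is undefined |

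Every participant has neck pain on entry, so one pain score at the end cannot isolate soreness after a session in week 1 or 2.

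**Visits per participant.**
- OMT: 3 × 3 = 9.
- BEMER: 5 × 3 = 15.
- OMT+BEMER: 9 OMT and 15 BEMER sessions. This is 15 visit days if OMT falls on BEMER days, and up to 9 + 15 = 24 if sessions are separate.
- Placebo: 9 light-touch and 15 sham sessions, if the schedule is read component by component.

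**OMT sessions followed by another visit within the expected window.** The protocol does not state weekdays. Assume weekday sessions at the same clock time, with BEMER Monday to Friday. There are C(5,3) = 10 ways to place three OMT days in a week, giving these results out of 9 OMT sessions:

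| Counting rule | OMT arm | OMT+BEMER arm | Monday/Wednesday/Friday |
|---|---|---|---|
| Visit at 24 to 48 h, 48 h included | 3 to 6 | 6 to 9 | 6 and 6 |
| Visit at 24 h up to but not including 48 h | 0 to 6 | 6 to 9 | 0 and 6 |

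With 48 h included, the two arms are equal in 4 of the 10 patterns. In the other 6, the combined arm has 3 more covered sessions.

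**Last session.** In the OMT arm no treatment visit follows the last of the 9 sessions under any pattern: 1/9 = 11%, or about 10 of 90 sessions. Whether the closing questionnaires fall in that window cannot be told from the text.

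**What full elicitation could show.** With no events among n participants, the one-sided 95% upper bound is 1 − 0.05^(1/n):
- n = 10: 1 − 0.05^(1/10) = 25.9%.
- n = 20 (both OMT arms): 1 − 0.05^(1/20) = 13.9%.

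The chance of at least one case among 10 is 1 − (1 − p)^10. For assumed true rates p of 5%, 10%, 20% and 30% this is 40%, 65%, 89% and 97%.

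**The case against.** The best defence is that the plan is not silent. Participants return questionnaires after treatment, and those ask about pain in every arm. An adverse effect confirmed by the physician leads to removal, so some cases would surface. De-identified data collection logs are mentioned, and Appendices B and D are not in the available text, so a form or contact instruction there cannot be excluded. Comparing harms is not a stated aim, and groups of 10 could not support it.

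Much of this stands, and it rules out several stronger readings that a reader might infer:

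- *No contact after the last session.* The closing questionnaires are a planned contact. Their timing is unspecified; they are not absent.
- *No symptom question at all.* The VAS and NDI ask about current pain. What is missing is a question about reactions to a session.
- *The harm goes uncounted.* Volunteered and confirmed cases can appear as removals.
- *Detection is shown to be uneven by arm.* This is an inference. On a Monday/Wednesday/Friday calendar, counting a 48-hour visit, coverage is 6 of 9 in both OMT arms.
- *The earlier low back pain study found nothing because nobody asked.* The documents do not say how that study collected harms.
- *The rising BEMER mat setting ("intensity 4 for week 2, and intensity 5 for week 3") adds to the problem.* The named reaction is tied to OMT, and the protocol expects none from BEMER.

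What the defence does not answer is that no route in the available text asks anyone about the one reaction the protocol expects.

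Two objections to the remedy also stand. Asking at every visit means more askings in the BEMER arms, so raw symptom counts would not be comparable. Asking may also bring more cases under the removal rule, chiefly in the OMT arms.

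**Conclusion.** The point holds in this form: on the available text, the reaction expected 24 to 48 hours after OMT is captured only if a participant volunteers it, and the reporting rule leaves it out. Detection could differ by arm because visits number 9 in the OMT arm and 15 in the BEMER arms. The second figure assumes that combined-arm OMT falls on BEMER days. The size of any difference cannot be fixed without the weekday pattern: depending on the pattern, coverage within 24 to 48 hours is 3 to 6 of 9 sessions in the OMT arm and 6 to 9 of 9 in the combined arm, and it can be equal.

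There is also a contradiction in the text. Analysis, III.A.3 and Research Participants, III.B anticipate no adverse effects, and III.B removes anyone who has one. Risks and Benefits, I.A.1 anticipates tenderness. Whether expected tenderness triggers removal is left undefined.

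This is a cheap improvement to safety capture. It does not invalidate the design, and correcting it would give an honest count rather than a powered comparison of harms.

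**What to change.** 1. **Reconcile first.** Before the item is used, the investigators should reconcile Analysis, III.A.3 and Research Participants, III.B with Risks and Benefits, I.A.1. Which clinical rule applies is for them to decide.
2. **Study Procedures and Timeline, II.A.3.** Add one self-completed item, labelled with study number only, at the start of every visit in all four arms: *Any new or worse symptom since your last session?* Record onset, duration and severity. Send the same item to every participant at least 48 hours after the last session.
3. **Risks and Benefits, I.C.** Record every answer regardless of arm or presumed cause, and make the answers available to the covering physician. Report by arm the number of participants with at least one symptom, rather than total reports, because the number of askings differs. This reduces the effect of unequal asking but does not remove it, so state the number of askings per arm beside the result.

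**Cost.** About a minute per visit, about 40 messages and an IRB amendment. More mild events will be recorded, and under the current removal rule there may be more removals in the OMT arms. Precision stays low at about 10 per group.

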## **Consent Process and Privacy Protection**

- I. Consent Process
- A. Participants will be introduced to the study through classroom announcements and recruitment emails. If they decide to participate we will provide participants with a written informed consent form (Appendix B) for them to read. In addition, a researcher will thoroughly explain the study to them to ensure that the subject is willing to participate in the experiment. The participant will then sign the form after comprehension is assessed via verbal reiteration and opportunity has been provided for questions.
- II. Privacy Protection/Confidentiality
- A. Any document that can be identified with the participant including informed consent, written contact information, and project data will be stored in a locked filing cabinet in the principal investigator's office. It will remain confidential unless provided with the participant's permission or required by law. Three years after completion of the study, any personal identifiers (names, addresses, birth dates, phone numbers, etc.) will be destroyed. A secured Google Drive account will be utilized to collect de-identified data throughout the study. Access to this account is exclusive to the Principal Investigator, Principal Co-

Investigator and designated medical students as identified in the IRB. All electronic submissions of de-identified data will be treated in the same manner as stated above regarding written information.

B. All participants will be given a numerical subject ID to ensure anonymity. Both recorded and survey data will be labeled with study number only. This ID will also be kept in a secured, locked filing cabinet, and only the Principal Investigator will have access to these documents. The materials will be saved for three years and then shredded.

C. Members of the research team have completed the required CITI training modules prior to working on the proposed research. Identity unlinking procedures and use of de-identified database ensure that the results of surveys and patient demographics remain confidential.

D. We will not be making any photograph, audio, or video recordings of participants without participant consent.

E. Our study does not involve collection of data that might produce a regulatory mandate or duty to inform authorities about potentially harmful or illegal activities.

F. Certification of Confidentiality and application for Federal Exemption to Reporting are unnecessary.

## **Payment and Costs**

### **I. Payment**

A. All subjects will receive a compensation of \$50 the form of a gift card for a local eating/shopping establishment at the time of completion of the study.

B. Subjects who cannot complete the protocol due to adverse events will still be compensated.

C. Subjects who are noncompliant with protocol will not receive compensation.

D. No fees for participation.

E. No penalties for participation or non-completion.

### **II. Costs**

A. Payment to subjects:

1. BEMER Pro Set: \$6410

2. 3 week compensation: \$50 per individual (estimating 40) = \$2,000

B. Total = \$8410

C. All paid by grants TBD

## **Appendices**

### **Appendix A: Recruitment email**

The LECOM Student American Academy of Osteopathy (SAAO), is conducting a study, and we would like to welcome all LECOM faculty, staff, and students to participate. The study will evaluate the individual and combined impact of osteopathic manipulative treatment (OMT) and Bio Electro-Magnetic Energy Regulation (BEMER) therapy on neck pain.

This study will take place over a three-week period. Each subject in the OMT group will receive treatment 3 times per week for a period of 3 weeks. Subjects in the BEMER groups will receive treatment 5 times per week for a period of 3 weeks. Each subject in the OMT+BEMER group will receive OMT 3 times per week and BEMER therapy 5 times per week for a period of 3 weeks. Subjects will complete brief questionnaires regarding neck pain and quality of life before the beginning of study and will complete the same questionnaires following the completion of the three week treatment. Each treatment will be individually scheduled with your assigned study coordinators. Each treatment session will last approximately 10-30 minutes.

You will be compensated with a \$50 gift card for your time.

If you are interested and would like to learn more about the study, please contact [name] at [[contact]](mailto:[contact]) for more information.

Thank you for your consideration in helping with this very important research.

